3.2.2 Secondary Outcome Measures

The first secondary outcome (mediator) will be change in the overall Illness Perception Questionnaire-Revised for Dental (IPQ-RD), cognitive (identity, consequences, timeline, cause, cure/controllability) representation subscale scores (Weinman et al. 1996; Barrowclough & Lobban 2001; Moss-Morris et al. 2002; Bonetti et al. 2010).

The other secondary outcome (mediator) will be a change in behavioral intention (Luzzi & Spencer, 2008; Ajzen, 1991, 2002). Behavioral intention will be assessed using a caregiver questionnaire and is measured by the summative score of 2 items (e.g., “I want to take my child to the dentist”, and “I plan to take my child to the dentist” on a 5 point scale (Luzzi & Spencer, 2008). The use of these measures will allow us to better understand the mechanisms of action of the intervention based on

our conceptual model. The change in IPQ-RD and behavioral intention scores will be calculated between baseline, two week, and final follow-up. A decrease in IPQ-RD scores (i.e. lower score) indicates better illness representation/perception, while increase in behavioral intention scores indicate a higher intention to take the child to dentist for follow-up care.

Table 3.2.1 Summary of measures, timeline, and source

Variable Type	Measure	Timeline ¹	Source
Exposure (Intervention Study Arms)	
 • CSM referral letter alone • CSM referral letter + DIG • Reduced CSM referral letter alone • Reduced CSM referral letter + DIG • Modified Standard letter 	At randomization	Mosleh et al. 2009 Ohio Department of Health Bureau 2007
Primary Outcome	Dental exams 
 • Child's receipt of dental care 	Beginning and end of school year	ICDAS (Pitts 2004)
Secondary Outcomes (Mediators)	IPQ-RD 
 • Caregiver illness perception Caregiver Questionnaire 
 • Behavioral intention 	Baseline, Two-week, and Exit	Barrowclough et al. 2001 Ajzen 2002; Conner & Armitage 1998
Moderators	Caregiver Questionnaire 
 • Caregiver literacy • Caregiver self-efficacy² • Caregiver dental fear • Caregiver perceived stress • Subjective norm² • Dental insurance status Site (urban/rural)	Baseline	Bennett et al. 2003 Finlayson et al. 2005 Humphris et al. 1995 Cohen & Williamson 1988 NHANES IV Ohio, Washington

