Confounders	Child's age, race, dental visit Caregiver socio-demographics (age, race, SES, education, marital status)	Baseline	NHANES IV
Subject compliance with Intervention	
 • Whether the referral letter (and DIG) was received (generic code) • Whether the referral letter (and DIG) was read/understood (Postcard) 	Within 2 days after Baseline dental exam	

1. **Baseline:** prior to screening dental exam; **At randomization:** after baseline dental screening exam; **Two-weeks:** Two weeks after randomization; **Exit:** two weeks before end of school year dental exam

2. Caregiver self-efficacy and subjective norms will also be considered as potential **mediators** in the additional mediational analyses, and will be measured at the **Exit** in addition to **Baseline**.

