Given the parameter estimates from the above models, we use a model-based standardization approach (Albert et al. 2011) to estimate relative risks (i.e., the ratio of the probabilities of dental usage for a given pair of interventions). A bootstrap approach will be used to obtain a 95% confidence interval for each relative risk. Significance will be determined using a gatekeeper approach to hypothesis testing. Specifically, we will first test for a difference in dental care receipt rates for S vs CSM+DIG (at the 0.05 nominal alpha level). If (and only if) this test is significant, we will proceed to test S vs. CSM alone and CSM vs CSM+DIG (both at the 0.05 nominal alpha level). We will use a similar approach for testing for each site. We will start by testing (for a given treatment comparison) an overall effect (stratifying over sites) at the 0.05 nominal alpha level. If (and only if) this is significant, we will then test (for the same treatment comparison) the effect within each site (at the 0.05 nominal alpha level). A 0.05 family-wise error level is attained in this approach assuming that a (true) effect for S vs. CSM+DIG implies a (true) effect for either S vs. CSM or CSM vs. CSM+DIG (or both), and that an overall effect implies an effect in one or both sites (which is logically the case).

To test the effect of the targeted component (timeline), we will fit the same multivariate generalized linear (specifically, logistic regression) models mentioned above with additional indicator representing reduced text.

Adjustment for Baseline Characteristics: Estimated intervention effects (described above) will be adjusted for the following baseline socio-demographic variables: child's age, race, and caregiver SES, education, and marital status.

Model Assumptions: We will assume that the probabilities of dental care receipt follow the selected logistic regression model (controlling for covariates) mentioned above. We assume that the outcomes for different caregivers (or different schools if a correlation structure for two cluster levels is used) are independent.

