In addition to assessing the overall effects of the interventions, we will investigate the mechanisms (or paths) through which interventions impact dental care receipt. As represented in Figure 1, we hypothesize that a significant portion of the intervention effect will occur via a three-link path: intervention will affect caregiver illness representation which will in turn affect behavioral intention which will in turn affect dental care receipt. Initially, we will consider an overall average score for caregiver illness representation and for behavioral intention. We have previously developed a generalized causal mediation analysis methodology (Albert and Nelson, 2011) which we can use to estimate and test this specific path effect. It is possible that other paths may also be involved – namely, a direct path (possibly involving unidentified mediators) from intervention to dental care receipt, and paths through either caregiver illness representation or behavioral intention alone. We will therefore decompose the overall effect, and estimate the contribution of each of the four possible paths. For each (broadly defined) mediator, we may be interested in examining multiple components (e.g., summary scores or factors representing specific constructs for caregiver illness representation, and the two questions of behavioral intention). We may thus handle each mediator in our model as multidimensional (that is, a vector of latent or observed variables). In addition, we will consider a further refinement of the model, and decomposition of the intervention effect, by allowing separate paths through the individual components of each mediator. The 2-week measurement time for the mediators reflects the hypothesized time of maximum impact of the intervention. However, we will make use of the 7-month measurements of the mediators to assess any changes in the effect of the intervention over time, as well as the relationship between the mediators (at alternative times) and dental care receipt.

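### The mediation models in Section 12.4 name no adjustment for baseline mediator scores or confounders, and the plan gives two forms of the mediator, so the split between direct and indirect paths can be biased

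*Combined protocol and SAP*

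**What the plan says.** Section 12.4 hypothesizes a chain from letter to illness representation to behavioral intention to receipt of care. It decomposes the overall effect into four paths with a cited causal mediation method, "which we can use to estimate and test this specific path effect". The form of the mediator is given as follows: "Initially, we will consider an overall average score for caregiver illness representation and for behavioral intention". On timing: "The 2-week measurement time for the mediators reflects the hypothesized time of maximum impact of the intervention". The mediation text names no covariates, no baseline mediator term, no assumption about mediator-outcome confounding and no sensitivity analysis. The supplementary self-efficacy analysis follows a similar model, so it inherits the gap.

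Four other places bear on this.

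- Section 3.2.2 labels both secondary outcomes as mediators and defines them as changes: "The change in IPQ-RD and behavioral intention scores will be calculated between baseline, two week, and final follow-up". Table 3.2.1 gives their timeline as "Baseline, Two-week, and Exit".
- The Confounders row of Table 3.2.1 reads "Child's age, race, dental visit Caregiver socio-demographics (age, race, SES, education, marital status", all measured at baseline. The row is not tied to any analysis and does not include baseline IPQ-RD or baseline intention.
- The adjustment rule in Section 12.4 comes before the mediation text: "Estimated intervention effects (described above) will be adjusted for the following baseline socio-demographic variables: child's age, race, and caregiver SES, education, and marital status".
- The questionnaire analysis in Section 12.4 includes selected baseline covariates, unlisted, in the regressions that compare mean scores across arms.

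**The concern.** Caregivers are randomized to letters, not to levels of illness perception or intention. A caregiver who was already motivated before the letter tends to score better at 2 weeks and may also be more likely to obtain care. Without the baseline score in the model, the association between the 2-week score and care mixes any effect of the mediator with this prior difference. The mixture is then multiplied by the letter's effect on the mediator and reported as an indirect effect.

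The secondary objective in the Protocol Summary is to understand the mechanisms of the new referral approach, and this is the analysis that serves it. A wrong split would credit, or deny, the theory behind the letter for the wrong reason. Omitting a baseline covariate from the randomized comparison of arms would not create confounding of this kind.

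**Working it through.** The plan states no sample size, power or error rate for the mediation analysis, so there is no figure of its own to reproduce. The one usable input is the standardized IPQ-RD difference in Section 12.2: 10/27 = 0.37 SD.

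**Inputs**

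- Letter effect on the mediator, a = 0.37 SD in the direction of improvement (Section 12.2; stated for IPQ-RD, with no figure given for intention).
- Control rate 19% and 204 caregivers per arm, so 408 in a two-arm comparison (Section 12.2).
- Assumed, not in the documents: correlation r between baseline and 2-week score, 0.3 to 0.6; log odds ratio u for care per SD of baseline attitude, 0.3 to 0.6; direct log odds ratio of the letter, 0.5.
- True effect of the mediator on care set to zero, so the true indirect effect is zero.

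**Approximate formulas.** Scores are standardized within arm.

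- Raw 2-week score, baseline omitted: its coefficient tends to u × r, so the false indirect effect is a × u × r on the log-odds scale.
- Change score alone: within arm its covariance with baseline is r − 1 and its variance 2(1 − r), so its coefficient tends to −u/2 and the false indirect effect is −a × u/2.
- If a = 0, both are zero.

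**Conversion to risk.** Control odds are 0.19/0.81 = 0.2346. With the letter they are 0.2346 × e^0.5 = 0.3867, a risk of 27.9%, so the total effect is 8.9 points. The mean of p(1 − p) over the two risks is (0.1539 + 0.2011)/2 = 0.1775. Example with r = u = 0.6: 0.37 × 0.6 × 0.6 × 0.1775 = 0.0236, or 2.4 points. Change score with u = 0.6: −0.37 × 0.3 × 0.1775 = −0.0197, or −2.0 points.

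**Simulation.** Linear mediator model and logistic outcome model. The indirect effect is in percentage points from 400,000 simulated subjects. The joint-significance test uses 408 caregivers and 1,500 runs. The true indirect effect is zero in every row.

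| r | u | Raw score, formula | Raw score, simulated | Change score, formula | Change score, simulated | Follow-up score with baseline covariate | False mediation, raw | False mediation, baseline covariate |
|---|---|---|---|---|---|---|---|---|
| 0.3 | 0.3 | 0.6 | 0.6 | −1.0 | −1.1 | 0.0 | 11% | 5% |
| 0.3 | 0.6 | 1.2 | 1.3 | −2.0 | −2.2 | 0.0 | not run | not run |
| 0.6 | 0.3 | 1.2 | 1.3 | −1.0 | −1.2 | about 0 | 32% | 6% |
| 0.6 | 0.6 | 2.4 | 2.5 | −2.0 | −2.2 | about 0 | 81% | 6% |

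Further results:

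- With no letter effect on the mediator, the raw-score indirect effect is 0.0 points and the test rejects in 4.7% of runs (r = u = 0.6).
- With a true indirect effect of 2.1 to 2.2 points and baseline attitude predicting care (u = 0.3 or 0.6), the raw score gives 2.9 to 4.5, the change score −1.1 to +0.1, and the baseline-adjusted model 2.1 to 2.3.
- The total effect does not depend on the choice. At r = u = 0.6 all three forms estimate 8.6 points.
- With the plan's 19% versus 37%, all of it direct, and correlation/odds ratio pairs of 0.4/1.35, 0.5/1.65 and 0.6/2.0, the raw score gives 1.0, 2.0 and 3.2 points, with false mediation in 14%, 55% and 86% of trials. Against the 18-point total, that is 1.0/18 = 6% to 3.2/18 = 18%. The change score gives −1.3 to −2.8 points. The baseline covariate gives about 0 points and 4% to 6%.
- With a smaller shift of 0.15 SD, the raw score gives 0.5 to 1.3 points and 9% to 29%.

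**The case against.** The best defense is that Section 12.4 is silent on adjustment and does not exclude it. Table 3.2.1 has a Confounders row. Since the exposure is randomized, such a row is most naturally meant for the non-randomized links. The questionnaire regressions already carry baseline covariates, Section 3.2.2 brings in the baseline score by subtraction, and the cited method may have its own covariate requirements. The Supplemental Materials list also names a separate statistical analysis plan whose text is not in the combined document.

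Much of this stands, and it rules out three stronger readings.

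- A reader might infer that the plan has decided against adjustment. It has not; the adjustment set is simply not stated for these models.
- A reader might infer that pre-existing attitudes will be counted as a path effect of the letter whatever the truth. Randomization balances those attitudes between arms. The bias needs the letter to move the mediator and baseline attitude to predict care independently. Its sign also depends on whether the mediator is the average score of Section 12.4 or the change of Section 3.2.2, which the documents leave open.
- A reader might infer that the trial's main result is at risk. Any bias moves effect between direct and indirect paths and leaves their total alone.

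The defense does not close the gap. The five-variable list covers effects described before the mediation text. The questionnaire regressions compare arms and do not link mediators to care. The Confounders row is assigned to no analysis and lacks both baseline mediator scores. Subtracting the baseline score does not cure the bias.

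The simulation has one fully observed mediator, whereas the plan's main path has two in sequence. The 2-week caregiver form asks the two intention items (question 1.6) only of caregivers who report neither a visit nor an appointment. The near-zero adjusted bias is therefore not shown for the intention path.

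**Conclusion.** The point holds as a gap in specification with a real consequence. The path models name neither the baseline mediator scores nor the confounders, and Sections 3.2.2 and 12.4 disagree on the form of the mediator. Under either form, without baseline as a covariate, the split is biased if the letter shifts the mediator and baseline attitude independently predicts care. The first condition is the plan's own hypothesis. The second is plausible but not documented.

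For a true indirect effect of zero and a shift of 0.37 SD, the illustrative size is about 0.6 to 3 points upward with a raw 2-week score, and about 1 to 3 points in the opposite direction with a change score alone. These sizes rest on the assumed correlation and odds ratio, on the IPQ-RD shift and on a single-mediator model. They show direction and range and do not predict this trial's result. The total effect and the primary analysis are unaffected, so this should be corrected but does not threaten the main conclusion.

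**What to change.** In Section 12.4, state for the path analysis that:

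- the mediator is the follow-up score, and baseline IPQ-RD and baseline intention are covariates in every mediator model and every outcome model;
- the same models include the Table 3.2.1 confounders (with the child's prior dental visit), dental insurance, perceived stress, literacy, dental fear and site;
- the estimates assume no unmeasured mediator-outcome confounding given these covariates, and a sensitivity analysis examines departures from that assumption.

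Reconcile the change-score definition in Section 3.2.2 with this. Switching to a change score alone would not be enough. Apply the same rule to the self-efficacy analysis, with its own baseline score.

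The cost is wording plus covariates already collected at baseline (Table 3.2.1 and the baseline questionnaires in Appendix C). Intervals for path effects may be slightly wider. Naming the set in advance also removes the choice of covariates after the data are seen.

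This does not by itself resolve the intention path. The plan also needs to say how 2-week intention is handled for caregivers who have already visited a dentist or made an appointment, since they are routed past those items.

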As a supplementary analysis, we will use measurements of self-efficacy (from the Caregiver Questionnaire given at 2 weeks and exit) to test the Health Belief Model as an alternative explanation for the effectiveness of the experimental intervention. Specifically, the mediation effect through self-efficacy will be assessed using a similar model and approach as described above. The relative contribution of the multiple hypothesized mediators will also be examined by including them together in a multiple mediator model.

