4. TAKING YOUR CHILD TO THE DENTIST

4a. The following questions are about taking your child to the dentist for any reason. Please circle the number that best fits your response.

	Strongly Disagree	Disagree	Neither disagree nor agree	Agree	Strongly Agree
4a1. I want to take my child to the dentist.	1	2	3	4	5
4a2. I plan to take my child to the dentist.	1	2	3	4	5

Study Site _____ ID# _____

Caregiver Questionnaire-Baseline

4b. The following questions are about how you would feel about taking your child to the dentist for preventive care (checkups, cleanings, topical fluoride) and dental treatments (fixing cavities). Please tell us how you feel by circling the number that best fits your response.

My feelings about the dentist will get in the way of taking my child to the dentist for...	Strongly Disagree	Disagree	Neutral	Agree	Strongly Agree
4b1. preventive care.	1	2	3	4	5
4b2. dental treatments.	1	2	3	4	5

4c.– 4d. The following questions are about what others think about taking your child to the dentist for preventive care and dental treatments. Please tell us how you feel by circling the number that best fits your response.

People important to me ...	Strongly Disagree	Disagree	Neutral	Agree	Strongly Agree
4c1. think that I should take my child to the dentist at least once a year.	1	2	3	4	5
4c2. would approve if I were to take my child to the dentist at least once a year.	1	2	3	4	5
4c3. take their child to the dentist at least once a year.	1	2	3	4	5
4d1. think that I should take my child to the dentist when a tooth problem is found.	1	2	3	4	5
4d2. would approve if I were to take my child to the dentist when a tooth problem is found.	1	2	3	4	5
4d3. take their child to the dentist when a tooth problem is found.	1	2	3	4	5

Study Site _____ ID# _____

Caregiver Questionnaire-Baseline

4e. Sometimes parents delay their child's dental care when other things get in the way. How likely are you to take your child to the dentist when the following happen to you? Please circle the number that best fits your response.

How likely are you to take your child to the dentist when you are ...	Very Likely	Moderately Likely	Somewhat Likely	Not At All Likely
4e1. under a lot of stress	1	2	3	4
4e2. depressed	1	2	3	4
4e3. anxious	1	2	3	4
4e4. feeling like you do not have the time (too busy)	1	2	3	4
4e5. tired	1	2	3	4
4e6. worrying about other things in your life	1	2	3	4

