32d. Diet or eating habits can cause cavities in a child	1	2	3	4	5
32e. Chance or bad luck can cause cavities in a child	1	2	3	4	5
32f. Poor dental care can cause cavities in a child	1	2	3	4	5
32g. Something a parent/caregiver does can cause cavities in a child	1	2	3	4	5
32h. A parent/caregiver's negative thoughts can cause cavities in a child	1	2	3	4	5
32i. Family problems or a parent/caregiver's worries can cause cavities in a child	1	2	3	4	5
32j. A parent/caregiver's feelings (feeling down, anxious) can cause cavities in a child	1	2	3	4	5
32k. A child's lack of ability to fight off infections can cause cavities	1	2	3	4	5

Site: _____ ID#_____

33. Please list in order the three most important things that you believe cause cavities in children. You may use any of the items from the previous question or you may have other ideas of your own.

[figure not shown]
The most important causes for me are:

1st _____

2nd _____

3rd _____

Family Access to Dentist Study

Study Site: _____ ID#: _____

Caregiver Questionnaire-2-week Follow-up

1. TAKING YOUR CHILD TO THE DENTIST**1.1 Did your child visit the dentist after the school dental screening?**

- a) Yes → Please GO TO Question 1.2
- b) No, but I have made an appointment with the dentist → Please SKIP TO Question 1.5
- c) No, and I have not made an appointment with the dentist → Please SKIP TO Question 1.6

If you answered YES to Question 1.1 above, please answer the following questions:

1.2 What is the name of the dental clinic / dentist where you took your child?

1.3 Did you take the referral letter (from the school dental screening) with you to the dentist?

- a) Yes
- b) No

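### The self-efficacy mediation analysis relies on 2-week data that the 2-week form does not collect; the exit values that remain could show a dental visit's effect on self-efficacy as mediation

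*Combined protocol and SAP*

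**What the plan says.** Section 12.4 (Final Analysis Plan) says of a supplementary analysis that "we will use measurements of self-efficacy (from the Caregiver Questionnaire given at 2 weeks and exit) to test the Health Belief Model". It applies a mediation model like the one for illness perception and behavioral intention, then enters the mediators together in a multiple-mediator model. No provision is made for the order of mediator and outcome.

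Footnote 2 to Table 3.2.1 (section 3.2.2) gives different times. Self-efficacy and subjective norms, as possible mediators, "will be measured at the Exit in addition to Baseline". No 2-week measure is listed.

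Section 12.4 names 2 weeks as the hypothesised time of greatest impact on the mediators. Of the later values of the main mediators it says "we will make use of the 7-month measurements of the mediators to assess any changes in the effect of the intervention over time", and it will also examine their relationship with receipt of care.

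**The concern.** A mediator has to come after randomisation and before the outcome it is meant to explain. If self-efficacy was not asked at 2 weeks, the baseline value is too early to be a mediator and the exit value follows most of the period in which care could be obtained. A caregiver who has taken the child to the dentist may then feel more able to do so. The arm with more visits would show higher exit self-efficacy, and within arms exit self-efficacy would predict care. A mediation model reads that pattern as an indirect effect, even when self-efficacy played no causal part.

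At stake is the trial's statement about mechanism: the test of the rival theory, and the comparison of mediators in a joint model in which some are measured at 2 weeks and one only at exit.

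**Working it through.** **Item check, Appendix C.** The forms do not label a self-efficacy scale. The evident block is the nine-item one headed "How likely are you to take your child to the dentist when the following happen to you".

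- Baseline form: items 4e1 to 4e9, 9 of 9 present, before randomisation.
- 2-week form: opens at item 1.1, "Did your child visit the dentist after the school dental screening", and ends at 1.7. It covers the visit, clinic, letter, treatment, what helped, intention and barriers. 0 of 9 present; the Spanish form is the same.
- Final form: items 3c1 to 3c9, 9 of 9 present.

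The belief items in section 2 of the baseline and final forms are also absent at 2 weeks, so the result does not depend on which block is called self-efficacy. The forms agree with the footnote, not with section 12.4.

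**Timing.** Table 3.2.1 puts exit two weeks before the final exam, and section 3.2.1 puts that exam 7 months after baseline. Taking 7 months as about 213 days, (213 − 14)/213 = 0.93 of the window has passed at exit. The final form also asks whether and in which month the child went (items 4.5 and 5.2), so any visit reported there precedes the self-efficacy answers on that form.

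**Size if a visit shifts the score.** The plan states no figure to reproduce. Inputs from sections 12.2 and 12.4: care rates of 19% (standard), 37% (CSM letter) and 57% (CSM letter + DIG), 204 per arm. Assumption: a visit raises exit self-efficacy by d SD. Model with no true mediation: care depends on arm only, and exit score = d × care + N(0,1). The mediation fit is linear for the score and logistic for care on arm and score.

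Share mediated: for small d it is close to d² × p₁(1 − p₁), where p₁ is the rate in the better arm. With p₁ = 0.57, p₁(1 − p₁) = 0.2451. This gives 0.04 × 0.2451 = 1% at d = 0.2, and 0.25 × 0.2451 = 6% at d = 0.5. At larger d the approximation runs high and the simulated values below apply. Both contrasts have 57% in the better arm, so one column of shares serves for both.

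False finding (both paths p < 0.05): the arm-to-score path is usually the limiting one. Its expected difference is d(p₁ − p₀), with variance [2 + d²{p₀(1 − p₀) + p₁(1 − p₁)}]/204. For 19% versus 57% at d = 0.5 the difference is 0.5 × 0.38 = 0.19, the SE is √(2.0998/204) = 0.1014 and z = 1.87, so P(Z > 1.96 − 1.87) is about 46%. At d = 1 the difference is 0.38, the SE is √(2.399/204) = 0.108 and z = 3.50, giving about 94%.

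| Assumed d | Spurious share | False finding, 19% v 57% | False finding, 37% v 57% |
|---|---|---|---|
| 0.2 | 1% | 5% | 3% |
| 0.3 | 2% | 16% | 7% |
| 0.5 | 6% | 46% | 16% |
| 0.75 | 12% | 78% | 29% |
| 1 | 20% | 95% | 43% |

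At d = 0 the rate is under 1%. Simulated rates vary by two or three points between runs. For 19% versus 37% they are about 3%, 6%, 13% and 29% at d = 0.2, 0.3, 0.5 and 0.8.

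**The case against.** The strongest reply is that the size rests on an unknown. The documents do not say how far a visit moves the score. At 0.2 SD the spurious share is about 1%, and at 37% versus 57% a false finding stays less likely than not even at 1 SD. This stands. A reader might infer that reverse causation is bound to count as mediation; the documents support only that it could.

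A reader might also infer that all care precedes the exit measure. The documents give no distribution of visit times, and some care may fall in the last two weeks. The figure of 93% is a share of the window, not of visits.

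A third tempting reading is that section 12.4 puts the 7-month illness perception and intention scores into the path decomposition. It does not say so. It uses them for change over time and for a relationship with care.

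It can be said, too, that the 2-week IPQ-RD has items on control (18 to 21). But section 12.4 names the Caregiver Questionnaire and treats self-efficacy as a separate mediator, so those items do not rescue the plan.

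Last, the analysis is labelled supplementary, and section 4.2 describes the extra mediation work as exploratory. That limits the reach of the problem. It does not remove the contradiction.

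**Conclusion.** The concern holds in a limited form. The 2-week part of the stated analysis cannot be run with the forms in Appendix C. The exit part can be run, but the plan has no safeguard against a visit's effect on self-efficacy being read as mediation. The distortion could be negligible or serious: a spurious share of about 1% to 20% for assumed shifts of 0.2 to 1 SD, with false-finding rates that depend on both the shift and the contrast. These figures assume no true mediation, normal scores of unit variance within care groups, full data on 204 caregivers per arm and no sibling clustering.

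What is affected is the Health Belief Model test and the multiple-mediator comparison. The primary comparison of dental care receipt is not touched.

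**What to change.** 1. Reconcile section 12.4, footnote 2 to Table 3.2.1 and Appendix C on when self-efficacy is measured.
2. Remove exit self-efficacy from the causal mediation and multiple-mediator models. Report it by arm, and describe its link with care as associational. This costs only wording.
3. Optionally, add a sensitivity analysis using the reported month of visit (final form item 5.2). It can show how the association varies with time since the visit. It cannot restore the order, because every visit reported there came before the form was filled in.
4. If the nine items are added to the 2-week form for second-year caregivers, state the limits. Section 5.3 places that recruitment in Ohio only, about 258 of 660 caregivers (258/660 = 39%), so Washington would contribute nothing. The form change needs IRB approval (section 15.2), and the two years would have different 2-week forms. Visits already made by 2 weeks (item 1.1) would also have to be handled.
5. Do not extend the by-arm report to exit intention. The final form asks it only in part 5B, of caregivers whose child did not visit, so the arms would be compared within groups selected on a reported version of the outcome. The 2-week form has a similar skip: intention is asked only where there is neither a visit nor an appointment. Restricting mediation to 2-week values therefore does not by itself settle intention.
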